### **Study Design**

#### **Aims 1&2**

- Experienced adult bone anchored implant recipients with either unilateral profound sensorineural hearing loss or conductive hearing loss will be enrolled for study. Subjects will be given the Adhear hearing system on trial for 2 weeks  $\pm$  90 days. Prior to dispensing of the experimental system, function of the subject's implant system will be verified. Custom pre-post subjective measures will be administered. Subjects will undergo behavioral measures of benefit in the 1) implant aided condition and 2) the Adhear Aided condition
- Conditions will be randomized by subject and will consist of the following:
  - Speech perception in noise ability using the BKBSIN (Etymotic, Elk Grove, IL) adaptive tests for speech front, noise front (0°/0° azimuth), speech poorer ear, noise better ear (90°/270° azimuth), speech better ear, noise poorer ear (90°/270° azimuth)
  - Soundfield aided narrow band signal thresholds – better ear plugged
  - Soundfield aided speech reception thresholds – better ear plugged
- At 2 weeks  $\pm$  90 days, subjects will undergo behavioral measures of benefit in the Adhear aided condition. Tests will be repeated using the subjects own processor on a soft headband to evaluate transcutaneous stimulation.
- Conditions will be randomized by subject and will consist of the following:
  - Speech perception in noise ability using the BKBSIN (Etymotic, Elk Grove, IL) adaptive tests for speech front, noise front (0°/0° azimuth), speech poorer ear, noise better ear (90°/270° azimuth), speech better ear, noise poorer ear (90°/270° azimuth)
  - Soundfield aided narrow band signal thresholds – better ear plugged
  - Soundfield aided speech reception thresholds – better ear plugged

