**Objective and behavioral outcome measures.**

- Data logging of device use
- Soundfield aided narrowband signal thresholds – better ear plugged
- Soundfield aided speech reception thresholds – better ear plugged
- Word recognition ability using PBK words and speech shaped noise at +5dB SNR for soft at 35, 45, and 55 dB for speech front, noise front (0°/0° azimuth)
- Aim 3a  
Pediatric unilateral conductive hearing loss patients who are between the ages of 2 and 17 years of age and are currently managed by the UMEI with a bone conduction device attached to a softband will be enrolled for study. Subjects will be given the ADHEAR bone conduction system on trial for 2 weeks  $\pm$  90 days. Subjects will be evaluated over 2 experimental visits.
  - VISIT 1: Assessment of subject's bone conduction device on the headband and initiation of ADHEAR trial
    - Prior to dispensing of the experimental system, function of the subject's current bone conduction device will be verified.
    - Subjective measures will be administered to determine benefit and satisfaction with the subject's own device on the headband.
    - Subjects will undergo behavioral measures of benefit with own bone conduction device on a headband
    - Subjects will be provided ADHEAR bone conduction hearing system
  - VISIT 2:
    - Subjective measures will be administered to determine benefit and satisfaction with the ADHEAR bone conduction hearing system
    - Subjects will undergo behavioral measures of benefit with ADHEAR bone conduction hearing system
    - ADHEAR system will be returned to the research site upon completion of the trial

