## **Data Management\***

Data collected includes: Gender, age, language, etiology and type of hearing loss, treatment ear, audiometric data including thresholds and speech outcomes, prior hearing treatment, date of activation or device use, aided thresholds, aided speech in noise performance, hours of device use, and subjective outcomes (see questionnaires included).

All the previously described data will be stored on the PI's computer and used for analyses purposes in room 526 of the clinical research building at the University of Miami Medical Center located at [name]. It will be password protected, and unique identifiers will be used for subject protection. Descriptive statistics will be used to report demographic (e.g. age and

gender) data. Quantitative data will be presented as mean, standard deviation (SD) and range (minimum and maximum); qualitative data will be presented as frequencies and percentages. Inferential statistics will be applied to detect differences in speech in noise performance as a function of transcranial attenuation. For this purpose, parametric Student's t-tests or nonparametric Wilcoxon signed rank tests will be performed, depending on the data distribution. Statistical significance will be set to  $p < 0.05$ . The subjective questionnaires will be summarized by visit using descriptive summaries. For numeric measures the change from baseline will be calculated and inferential tests applied. For categorical measures, a shift from baseline will be presented demonstrating the subjects as being better, the same, or worse.

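### No aim names a primary outcome or device contrast, and an unadjusted p < 0.05 covers several tests, so the measure that decides each aim is left open

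*Combined protocol and SAP*

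**What the plan says.** Data Management holds the whole analysis plan. It names two families of tests.

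- **Performance:** "Inferential statistics will be applied to detect differences in speech in noise performance as a function of transcranial attenuation". The method is that "parametric Student's t-tests or nonparametric Wilcoxon signed rank tests will be performed, depending on the data distribution". The level follows: "Statistical significance will be set to" p < 0.05, with sidedness not stated.
- **Questionnaires:** "For numeric measures the change from baseline will be calculated and inferential tests applied". Categorical items are not tested: "For categorical measures, a shift from baseline will be presented demonstrating the subjects as being better, the same, or worse".

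The outcomes are listed elsewhere.

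- **Aims 1 and 2** (Study Design): "Speech perception in noise ability using the BKBSIN" in three speech and noise configurations, then "Soundfield aided narrow band signal thresholds" and speech reception thresholds. The implant and Adhear conditions are tested first. A second session tests Adhear and the subject's own processor on a soft headband.
- **Aim 3** (Objective and behavioral outcome measures): device use, aided thresholds, speech reception, and "Word recognition ability using PBK words and speech shaped noise at +5dB SNR for soft at 35, 45, and 55 dB". Child and guardian questionnaires are added under Subjective outcome measures.

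Under Objectives, Aims 1 and 2 hypothesise similar benefit. Aim 3 hypothesises greater benefit on both objective and subjective grounds. No section ranks the outcomes, sets a testing order or adjusts for multiple tests.

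**The concern.** A significance level is a decision rule only once it is clear which test decides. Here neither the outcome nor the comparison is fixed. The performance analysis is framed around transcranial attenuation and the questionnaire analysis around change from baseline. Neither is the Adhear-versus-comparator contrast that the aims are about.

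The consequence depends on the aim. In Aim 3 a significant difference supports the hypothesis, so several unadjusted tests raise the chance that at least one supports it by luck. In Aims 1 and 2 a significant difference counts against the hypothesis. The exposure there is the reverse: with small groups and several measures, some will probably be non-significant, and those can be cited as showing similarity.

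**Working it through.** The documents give no power, effect size, standard deviation, similarity margin or familywise rate, so there is no figure of the plan's own to reproduce.

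**Inputs from the documents**
- Level 0.05 per test (Data Management); two-sided is assumed.
- Three PBK levels in noise for Aim 3; three BKB-SIN configurations for Aims 1 and 2.
- At least 10 and at most 30 participants per group (Procedures Involved); at most 15 for Aim 3 (Consent Process).

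**Assumed inputs**
- One score and one contrast for each of the child and guardian questionnaires. The documents do not give the number of scores.
- Correlation between tests of 0 to 0.8.
- A true paired difference of 0.5 SD for the similarity check.

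**Aim 3: chance of at least one false positive**

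For k independent tests this is 1 − 0.95^k. Only the two families named in Data Management are counted: 3 PBK levels + 2 questionnaire scores, k = 5.

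1 − 0.95^5 = 1 − 0.774 = 22.6%.

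Correlated paired t-tests were simulated with n = 10 and 40,000 runs:

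| Correlation | Any false positive, k = 5 | In the direction favouring Adhear |
|---|---|---|
| 0 | 22.6% | 12.0% |
| 0.5 | 19.3% | 9.7% |
| 0.8 | 13.5% | 6.8% |

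If device use, aided thresholds (as one score) and speech reception were also tested, k = 8 and 1 − 0.95^8 = 33.7%. By simulation it is 26.1% at correlation 0.5 and 16.8% at 0.8. The plan does not say whether they are.

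**Aims 1 and 2: chance that a real difference is missed**

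For one paired t-test the noncentrality is 0.5 × √n.
- n = 10: 0.5 × 3.162 = 1.58; power 29.3%, so non-significant 70.7% of the time.
- n = 30: 0.5 × 5.477 = 2.74; power 75.4%, so non-significant 24.6% of the time.

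Suppose the same 0.5 SD difference holds in all three BKB-SIN configurations. If the tests were independent, the chance that at least one is non-significant would be:
- n = 10: 1 − 0.293³ = 97.5%.
- n = 30: 1 − 0.754³ = 57.1%.

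If the three tests were perfectly correlated, the figures would be the single-test values, 70.7% and 24.6%. With equal effects and positive correlation the chance lies between these limits. So even at 30 per group, a measure available to cite for similarity is common when a moderate difference is real.

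**The case against.** A reader might infer that every outcome, configuration and visit is tested at 0.05, and count two dozen or so tests in Aims 1 and 2. The documents do not support that. Data Management names tests only for speech in noise and numeric questionnaire change. Thresholds, speech reception and device use are assigned no test. The number of narrowband frequencies is not given for the outcomes; the four listed frequencies belong to eligibility. The device contrasts are not enumerated. What stands is that the tested set is undefined.

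A reader might also infer that every aim has a large false-positive risk. That fits Aim 3. In Aims 1 and 2 a false-positive difference works against the stated hypothesis, and Aim 3a, which evaluates validity, has no stated direction.

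Three further points are fair. The outcomes come from the same subjects, so correlation lowers the inflation. The two-sided rate overstates errors favouring Adhear by about a factor of two. No section says that one significant measure would suffice for Aim 3, and its hypothesis can be read as needing both objective and subjective benefit. These points reduce the figure but do not supply the missing rule: even at correlation 0.8 the two-sided rate is 13.5% against a nominal 5%.

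**Conclusion.** The point holds in this limited form. No aim has a named deciding outcome or device contrast, the 0.05 level is unadjusted, and the set of tested outcomes is unclear. For Aim 3 the chance of at least one false positive is about 23% for five independent tests, or 14% to 19% at correlation 0.8 to 0.5, and about half that favouring Adhear. This assumes one child and one guardian score and two-sided testing. For Aims 1 and 2 the fault is room for selective emphasis on non-significant measures. Its size depends on the assumed true difference and on the group size reached. The plan should be amended before analysis; the design itself is not affected.

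**What to change.** In Data Management, before analysis, name one device contrast and its primary outcome for each aim, and state which other outcomes are tested.

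- **Aims 1 and 2:** one BKB-SIN configuration, Adhear versus implant, stating which Adhear session is used. Report the paired difference with a confidence interval. State that non-significance alone is not evidence of similarity; a similarity conclusion would also need a margin set in advance. Do not use Holm adjustment here, because it makes non-significance, and so an apparent similarity, easier to reach.
- **Aim 3:** Adhear versus headband device on the PBK score averaged over the three levels, together with one questionnaire total at the end of each phase. Require both to succeed, to match the two-part hypothesis. Each is tested at 0.05, and the chance of a false claim of both stays at or below 5%.
- **Aims 3a and 3b:** a primary outcome that every enrolled child can provide. PBK alone is unsuitable: enrolment starts at age 2, and the unilateral protocol substitutes a detection task for children who cannot repeat words reliably. The aided threshold averaged over frequencies is a candidate, if the investigators confirm that all children can complete it. For bilaterally affected children, also name which fitting is compared.
- **All other outcomes:** estimates with confidence intervals and no significance claim, or Holm adjustment for Aim 3 only.

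The change is wording only, with no added subjects or visits. The downside is that fewer outcomes can carry a significance claim. Requiring both Aim 3 outcomes also lowers power. With an assumed 0.8 SD effect on each, one test succeeds 61.6% of the time at n = 10 and 82.1% at n = 15. If the two were independent, both would succeed 0.616² = 37.9% and 0.821² = 67.4% of the time; positive correlation raises these.

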## Objectives\*

Aim 1. Determine if non-invasive Adhear is an equally effective treatment solution for unilateral profound sensorineural hearing loss when compared to invasive boneanchored implants.

Hypothesis: We hypothesize that non-invasive Adhear bone conduction technology will provide similar benefit to the more invasive bone anchored implant system for unilateral profound sensorineural hearing loss.

Aim 2. Non-invasive Adhear is an equally effective treatment solution for conductivehearing loss when compared to invasive bone anchored implants.

Hypothesis: We hypothesize that non-invasive Adhear bone conduction technology will provide similar benefit to the more invasive bone anchored implant system for conductive hearing loss.

Aim 3. Non-invasive Adhear is a more effective treatment solution for pediatric hearing loss when compared to bone conduction devices worn on a headband.

Hypothesis: We hypothesize that non-invasive Adhear bone conduction technology will increase objective and subjective benefit when compared to traditional bone anchored implant processors worn on a headband for pediatric conductive hearingloss.

Aim 3a. - To evaluate the validity of the non-invasive ADHEAR bone conduction hearing system in children with bilateral or unilateral conductive hearing loss

Aim 3b. To compare the benefits of the non-invasive ADHEAR bone conduction hearing system in children with bilateral and unilateral conductive hearing loss to traditional non- invasive bone conduction hearing systems worn on a headband.

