## **Inclusion and Exclusion Criteria\***

All subjects will be prospectively enrolled for study.

Aims 1 and 2 will include adult English speaking patients who are experienced users of BAIs for the

indication of either single sided deafness or conductive hearing loss. Experienced will be defined as greater than 6 months of device use and no intermittent function of the device within 2 weeks of enrollment. Aims 1 and 2 will require retrospective chart review to identify potential study subjects for recruitment. Subjects who spontaneously present to the clinic may also be enrolled should the meet inclusion criteria. Subjects will be limited to those who have normal hearing by bone conduction defined as a pure tone average of 25 dBHL or better at 500, 1000, 2000, & 3000 Hz in at least one ear.

Aim 3 will include English speaking children 5 to 17 years of age and their primary guardian who present to the clinic for treatment by BAI on a headband device for the indications of single sided deafness or conductive hearing loss. Because subjects for aim 3 have not previously been users of a BAIs, subjects for aim 3 will be recruited during spontaneous presentation to the clinic. Subjects will also be recruited for aim 3 from various sites using flyers and email. Subjects will be limited to those who have no prior use of a BAI or bone conduction hearing device, normal hearing by bone conduction defined as a pure tone average of 25 dBHL or better at 500, 1000, 2000, & 3000 Hz in at least one ear. For those children where this cannot be definitively established, children will be included who display clinical signs of normal bone conduction hearing beyond a reasonable doubt and may include such evidence as (but not limited to): auditory brainstem response, speech awareness thresholds, visual reinforcement audiometry, conditioning play audiometry, CT scans, etc.)

Aims 3 a & b are an extension of Aim 3 and will include pediatric bilateral or unilateral conductive hearing loss patients who are between the ages of 2 and 17 years of age and are currently managed by the UMEI with a bone conduction device attached to a softband will be enrolled for study.

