### **Study Populations**

- Minimum of 10 established adult unilateral profound sensorineural hearing loss recipients of bone anchored implants
- Minimum of 10 established adult conductive hearing loss recipients of bone anchored implants
- Minimum of 10 new pediatric headband bone conductive device candidates.
- Minimum of 10 guardians of the pediatric population involved
- Minimum of 15 established pediatric unilateral conductive hearing loss patients currently fit with a bone conduction device on a softband.
- Minimum of 10 established bilateral conductive hearing loss patients currently fit with a bone conduction device on a softband.

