#### **Aim 3**

- Pediatric conductive hearing loss patients who are between the ages of 5 and 15 years of age and present to the UMEI hearing rehabilitation by bone conduction technology along with their primary guardian will be enrolled for study. Subjects will be evaluated in two phases:
  - Phase 1 – random assignment to trial with either a traditional bone conduction

device on a headband or an Adhear hearing system for 3 weeks  $\pm$  90 days. Pediatric and parent subjective questionnaires will be administered prior to and at the end of phase 1.

- Phase 2- trial with system alternate to that which was assigned for phase 1. Pediatric and parent subjective questionnaires will be administered prior to and at the end of phase 2.

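### Aim 3 asks whether children benefit more from Adhear than from a headband device, but the questionnaire analysis specifies no Adhear-versus-headband contrast.

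*Combined protocol and SAP*

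**What the plan says.** **Hypothesis.** Under Objectives, Aim 3 states that "non-invasive Adhear bone conduction technology will increase objective and subjective benefit when compared to traditional bone anchored implant processors worn on a headband". This is a comparison of two devices.

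**Design.** Study Design, Aim 3, describes phase 1 with the words "random assignment to trial with either a traditional bone conduction"; the alternative is Adhear, and the conventional device is worn on a headband. Each child then uses the other device in phase 2. This is a two-period crossover. Inclusion and Exclusion Criteria adds for Aim 3: "Subjects will be limited to those who have no prior use of a BAI or bone conduction hearing device".

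**Size.** Study Populations gives "Minimum of 10 new pediatric headband bone conductive device candidates", and Consent Process caps Aim 3 at 15.

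**Questionnaires.** Subjective outcome measures places them before and at the end of each phase, for child and guardian. The form used before a device is assigned stops at question 15 (guardian) or 18 (child), because later items concern the device. The complete form is used at the end of both phases.

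**Analysis.** Data Management has three elements for the questionnaires:
- Numeric scores: "For numeric measures the change from baseline will be calculated and inferential tests applied", with neither the baseline nor the test identified.
- Categorical items: the plan is that "a shift from baseline will be presented demonstrating the subjects as being better, the same, or worse", again without saying which form is the starting point.
- Overall presentation: "The subjective questionnaires will be summarized by visit using descriptive summaries", so the grouping is not by device.

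The t-test and Wilcoxon signed rank test are named for another purpose: "Inferential statistics will be applied to detect differences in speech in noise performance as a function of transcranial attenuation".

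**The concern.** The design supplies what Aim 3 needs, namely two end-of-phase scores per child, one on each device, in random order. The analysis section does not say that they will be compared. Its planned quantities describe change over visits or change from a starting point that it does not define.

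A report that followed this text could show that children improved with bone conduction without saying whether Adhear was better. The contrast would then have to be chosen after the data were in hand. One option open at that stage is to test each device against baseline and compare the two verdicts. That is not a test of the difference between devices, and its error rate is uncontrolled.

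**Working it through.** The plan gives no effect size, SD or power for Aim 3, so it has no figure to reproduce. Step 1 sets the planned quantities against the hypothesis. Steps 2 and 3 are illustrations on stated assumptions.

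**Step 1. What each planned quantity estimates.** Let a and h be the mean gains over no device for Adhear and headband, and p a period effect (phase 2 minus phase 1). Assume equal numbers in each order and no carryover.

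| Quantity | Adhear first | Headband first | Average by visit |
|---|---|---|---|
| End of phase 1, change from pre-assignment form | a | h | (a + h)/2 |
| End of phase 2, change from pre-assignment form | h + p | a + p | (a + h)/2 + p |
| Phase-2 change from the form before phase 2 (if it reflects the first device) | h − a + p | a − h + p | p |

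The device difference a − h cancels from every by-visit average.

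- If baseline is the pre-assignment form, each change is a gain over no device. The device-specific items have no value on that form, so no such change exists for them.
- If baseline is the form before each phase, the phase-2 change starts after use of the first device. It then holds the device difference with opposite signs in the two orders, plus p.

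Half the difference between the two orders in the last row is [(a − h + p) − (h − a + p)]/2 = a − h. The design can therefore estimate the Aim 3 quantity; the analysis text does not ask for it.

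**Step 2. Comparing two separate tests.** Assumptions: equal devices, normal change scores with SD 1, correlation 0.3-0.7 between a child's two changes, and a one-sample t-test per device at two-sided 5% (the plan does not state sidedness). Results are from 200,000 simulated trials per cell. The chance that only Adhear is significant is P(Adhear significant) − P(both significant). For n = 10 and a gain of 1 SD this is 0.803 − 0.666 = 0.137 at correlation 0.3, and 0.803 − 0.710 = 0.093 at 0.7.

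| Gain on both devices (SD) | Only Adhear significant, n = 10 | n = 15 |
|---|---|---|
| 0.5 | 12-18% | 13-20% |
| 0.7 | 14-21% | 11-17% |
| 1.0 | 9-14% | 3-4% |
| 1.5 | about 1% | under 0.1% |

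A direct two-sided 5% test wrongly favours Adhear in 2.5%.

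**Step 3. Power of the direct contrast.** Take period differences within child and compare the two orders by a two-sample t-test with n − 2 degrees of freedom. For a true difference d, in SDs of the within-child difference, the noncentrality is d / √[¼(1/n₁ + 1/n₂)]. That is 3.162d for 5:5 and 3.864d for 8:7.

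| d | n = 10 (5:5) | n = 15 (8:7) |
|---|---|---|
| 0.5 | 29% | 43% |
| 0.8 | 60% | 82% |
| 1.0 | 79% | 95% |

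**The case against.** The strongest reply is that the contrast is unspecified, not ruled out. The tests on change scores are unnamed, and the same paragraph mentions a paired test. With a common pre-assignment baseline, testing one device's change against the other's is the direct contrast for guardian items 1-15 and child items 1-18. This stands: a reader might infer that the plan excludes a device comparison, and the text does not say so. But the sentence attaches its tests to change from baseline and names no second device, so the comparison is not planned either.

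Four further inferences are not supported:
- **That device-specific items can be compared only between the two end-of-phase forms.** Only the pre-assignment form is described as shortened. The content of the form before phase 2 is not stated.
- **That two equal devices would usually both be significant against baseline.** With n = 10 this happens in 67-71% of trials at a gain of 1 SD, but in only 30-37% at 0.7 SD.
- **That comparing two separate tests always inflates error.** The table in the working shows it above 2.5% at intermediate gains and below it at large ones. Nor do the documents say that anyone intends this comparison.
- **That the gap extends to Aims 3a and 3b.** There visit 1 is scored on the child's own headband or softband device, so change from visit 1 already compares devices.

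It is also fair to say that the direct contrast is no guarantee of an answer. With 10-15 children it has low power for a difference of 0.5 SD.

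**Conclusion.** The point holds. For the Aim 3 questionnaires, the plan specifies by-visit summaries that mix the devices and change or shift from an undefined baseline. Under neither reading of baseline does the analysis as written test whether Adhear gives more subjective benefit than a headband device. This conclusion comes from the text and does not depend on the simulations.

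The numerical size is illustrative. It assumes normal scores (the questionnaires are not visible here), an SD of change of 1 and correlations of 0.3-0.7. On those assumptions, inferring superiority because only Adhear is significant would be wrong in roughly 9-21% of trials at n = 10, and 3-20% at n = 15, for gains of 0.5 to 1.0 SD. The data remain usable and the omission can be repaired, so this is a change that should be made rather than a fatal flaw.

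**What to change.** Add to Data Management, for Aim 3 only:

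> For Aim 3, child and guardian questionnaire scores at the end of phase 1 and phase 2 will be compared within child, Adhear minus headband, allowing for period (two-sample t-test of period differences by order of devices, or its exact permutation version; one to be chosen before data are seen). Categorical items will be tabulated within child as better on Adhear, same, or better on headband. Summaries will be given by device as well as by visit. For Aim 3, baseline is the pre-assignment questionnaire; change from it (guardian items 1-15, child items 1-18) is secondary and describes benefit over no device.

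The baseline sentence must stay limited to Aim 3. Aims 3a and 3b have no pre-assignment form of this kind, and their visit 1 serves a different purpose.

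**Cost.** No new data are needed, because the complete questionnaire is already collected at the end of both phases. Change from baseline becomes secondary. The period term costs one degree of freedom: for a difference of 1 SD at n = 10, power goes from 80% to 79% with order balanced 5:5, and to about 72% if order falls 7:3. The permutation version has about 77% at 5:5.

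Blocked and concealed assignment of order, a choice between child and guardian as primary respondent, and a statement on carryover would help, but they are separate and optional.
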